3.3.3 Definition and Management of MG Worsening

During the study, MG worsening will be defined as:

• QMG score increase by ≥ 4 points relative to Baseline/Week 0

During the CS Tapering phase, if a subject meets the definition of MG worsening as defined above, then the following increase in CS dose will occur as shown in Table 3-3 and Table 3-4:

Table 3-3 *Daily* CS Dose Increase in Response to Worsening MG (CS Tapering Phase Only) (prednisone equivalent)

CS Dose (mg/day) at Which Worsening Occurs	Dose Increase (mg/day)
≥ 15	20
< 15	15

Table 3-4 Every Other Day CS Dose Increase in Response to Worsening MG (CS Tapering Phase Only) (prednisone equivalent)

Every Other Day CS Dose (mg/every other day) at Which Worsening Occurs	Every Other Day Dose Increase (mg/every other day)
≥ 30	40
< 30	30

If an episode of MG worsening fails to improve with the above CS dose increase within 6 weeks (by the second subsequent visit), or if another specific episode requires a second dose increase at any time, the subject will be withdrawn from the study. Also see Early Discontinuation Visit (Section 3.8.2.6 and Section 3.11).

Special Note for subjects tapered to 0 mg CS per day: Some subjects with MG are uniquely sensitive to complete CS withdrawal (0 mg prednisone equivalent daily), and may become more vulnerable to MG triggers and sudden MG exacerbations. Therefore if a subject has tapered to 0 mg prednisone equivalent daily, any worsening MG signs or symptoms must be evaluated in clinic as soon as possible (recommended within 24 hours, allowed up to 48 hours) and treated aggressively with CS dose increase as delineated in the tables above. Once tapered to 0 mg CS per day, a 4-point QMG increase from Baseline/

Week 0 is not required for re-initiating CS because deterioration can be of greater severity and speed than expected and may be difficult to reverse.

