3.3.5 Myasthenic Crisis

Myasthenic (or MG) crisis will be defined as an episode of worsening (as defined in Section 3.3.3) which requires hospitalization. Hospitalizations solely for socioeconomic reasons would not fulfill criteria for MG crisis. Also see Early Discontinuation Visit (Section 3.8.2.6 and Section 3.11).

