4.4.6 Seriousness of Adverse Event or Suspected Adverse Drug Reaction, Serious Adverse Event

An AE or suspected ADR is considered "serious" if, in the view of either the investigator or Sponsor, it results in any of the following outcomes:

- 1. Death
- 2. Life-threatening AE (life-threatening in the definition of "serious" refers to an event in which the subject was at risk of death at the time of the event; it does not refer to an event which hypothetically might have caused death if it were more severe)
- 3. In-patient hospitalization or prolongation of existing hospitalization
- 4. A persistent or significant incapacity or substantial disruption of the ability to conduct normal life functions
- 5. A congenital anomaly/birth defect
- 6. An important medical event (important medical event in the definition of "serious") refers to those events which may not be immediately life-threatening, or result in death, or hospitalization, but from medical and scientific judgment may jeopardize the subject or/and may require medical or surgical intervention to prevent one of the other outcomes listed above

This definition permits either the Sponsor or the investigator to decide whether an event is "serious." If either the Sponsor or the investigators believes that the event is serious, the event must be considered "serious" and evaluated by the Sponsor for expedited reporting.

A distinction should be drawn between serious and severe AEs. The term "severe" is used to describe the intensity (severity) of a specific event; the event itself, however, may be of relative minor medical significance (such as severe headache). This is not the same as "serious," which is defined on subject/event outcome or action criteria usually associated with events that pose a threat to a subject's life or functioning. Seriousness (not severity) is a medical term while severity is a subjective term.

According to the medical criteria, an AE or a suspected ADR can be classified as serious, although it does not fulfill the conditions fixed in this section, if it is considered important from a medical point of view.

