4.4.6.1 Hospitalization or Prolongation of Hospitalization

An AE or suspected ADR is considered "serious" if, in the view of either the investigator or Sponsor, it results in hospitalization or prolongation of hospitalization UNLESS this hospitalization or prolongation of hospitalization is part of the clinical practice (according to the investigator's criteria) for the treatment of the MG.

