4.4.7.3 MG Events That Are Not Considered AEs

Given that variations in symptoms are an inherent part of the natural history of MG, all recorded information regarding severity of MG manifestations will be considered efficacy data.

For the purpose of this study, variation in MG symptoms will not be considered an AE unless an exacerbation of MG, or MC requires hospitalization. If a subject is hospitalized for MG, it will be reported as an SAE.

4.4.8 Procedures for Eliciting Reports of and for Recording and Reporting Adverse Events and Suspected Adverse Drug Reactions

The occurrence and follow-up details of all AEs experienced by any of the subjects during the clinical trial, from signature of the *Clinical Trial Written Informed Consent Form* to the last follow-up visit, will be recorded on the AE eCRF entry and in the subject's medical record. If no AE has occurred during the study period, this should also be indicated in the eCRF.

At each visit, AEs will be elicited by asking the individual a non-leading question such as "Do you feel different in any way since the last visit?" Moreover, AEs will also be collected through directly observed events or spontaneously volunteered by the subject. Clearly related signs, symptoms and abnormal diagnostic procedures should preferably be grouped together and recorded as a single diagnosis or syndrome wherever possible. It is responsibility of the investigator to ensure that AEs are appropriately recorded.

The following variables must be recorded on the AE eCRF entry:

- 1. the verbatim term (a diagnosis is preferred)
- 2. date/time of onset
- 3. date/time of resolution
- 4. severity (mild, moderate, severe)
- 5. causality (unrelated, doubtful/unlikely, possible, probable, definite)*
- 6. seriousness (yes, no)
- 7. action taken (with regard to IP)
- 8. other action (to treat the event)
- 9. outcome and sequel (follow-up on AE) *AEs occurring before subject's exposure to IP will be always labeled as "unrelated."

For AEs that occur during infusions, the infusion rate in effect at the time of onset of the AE, the time of onset of the AE and the time of AE change materially in intensity and/or resolves will be captured the eCRF entry.

In addition to the investigator's own description of the AEs, each AE will be encoded by the Sponsor or CRO according to the Medical Dictionary for Regulatory Activities (MedDRA®).

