4.4.9 Timelines and Reporting of Serious Adverse Events

Any SAE (see Section 4.4.6) that occurs after signing the ICF through the last day of subject's participation in the clinical trial must be expeditiously reported whether or not considered attributable to the study drug. Each SAE must be fully recorded in the subject's eCRF or SAE Report Form.

SAEs will be reported using the designated SAE Report Form. When the investigator becomes aware of an SAE, she/he must submit electronically through the electronic data capture (EDC) system or when the EDC system is not available submit a completed, signed and dated SAE Report Form (in English) within 24 hours to the Sponsor by email/fax.

Each SAE must be followed up until resolution or stabilization. After the initial report, all relevant information for SAE follow up, and for the outcome, must also be supplied to the Sponsor in a timely manner (within 3 days from its identification or within 24 hours for relevant new information) by means of the SAE Report Form. In addition, the Sponsor or CRO may request additional information and/or reports.

All SAE Report Forms must be reported to Grifols electronically through the EDC system or when the EDC system is not available, reported to:

When required, and according to local law and regulations, SAEs must be reported to the IRB/EC and regulatory authorities.

4.4.10 Type and Duration of the Follow-Up of Subjects after Adverse Event or Suspected ADR

In so far as is possible, all individuals will be followed up until the AE or suspected ADR has been resolved. If an AE/suspected ADR/SAE is present when the subject has completed the study, the course of the event must be followed until the final outcome is known or the event has been stabilized and no further change is expected and the investigator decides that no further follow-up is necessary.

Any pregnancy must be followed by the investigator until delivery or to the end of pregnancy.

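### SAP 7.3 sends some MG-worsening discontinuers to LOCF although Protocol 5.1.3.1 makes all of them non-responders; secondarily, Protocol 4.4.6.1 and 4.4.7.3 disagree on whether an MG admission is serious

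*Protocol*

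**What the plan says.** **Primary endpoint.** Protocol 5.1.3.1 (and the synopsis) counts subjects who leave early because of MG worsening as not reaching the 50% reduction. It attaches no adverse-event or admission condition, and it keeps LOCF for other reasons. Protocol 3.3.3 holds a withdrawal rule that produces such subjects, with two triggers. The first reads: "If an episode of MG worsening fails to improve with the above CS dose increase within 6 weeks (by the second subsequent visit". The second is a further episode that needs another dose increase. Neither route requires admission.

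SAP 7.3 replaces the non-responder rule with WOCF for subjects who meet all of four criteria:
- one of four listed discontinuation reasons, including one for MG crisis needing hospitalisation and one for MG worsening that is steroid-unresponsive or a second episode;
- at least one adverse event with an MG preferred term;
- that event is serious because of hospitalisation or death;
- that event is treatment-emergent.

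Everyone else gets LOCF. SAP 16.1.2 and 16.2.2.1 use the same group. SAP 3.3 lists only the ITT-to-mITT change.

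**When worsening is an adverse event.** Protocol 4.4.7.3: "variation in MG symptoms will not be considered an AE unless an exacerbation of MG, or MC requires hospitalization".

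**Seriousness of MG admissions.** Protocol 4.4.6.1 makes an event serious if it leads to hospitalisation, "UNLESS this hospitalization or prolongation of hospitalization is part of the clinical practice" for treating MG, as the investigator judges. Protocol 4.4.7.3: "If a subject is hospitalized for MG, it will be reported as an SAE". Item 3 of 4.4.6 lists "In-patient hospitalization or prolongation of existing hospitalization" without exception. SAP 16.3.1.6 and 16.3.1.7 count a crisis or inpatient worsening only through an MG adverse event that is serious for hospitalisation.

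**The concern.** The SAP names steroid-unresponsive or second-episode worsening as a reason that leads to WOCF, and then adds a condition that an outpatient withdrawal does not itself generate. The listed reason therefore has no effect for a subject who never had an MG admission and did not die of MG. That subject is a treatment failure under the protocol, but under the SAP is scored on the last recorded steroid dose. If that dose is at or below half of baseline, the primary analysis counts a success. The secondary percent-reduction endpoint takes the same LOCF value.

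The smaller issue is that two protocol sections can classify the same MG admission differently, with no stated precedence, and about 40 centres may read them differently. An admission left unflagged drops out of both exploratory inpatient endpoints. If that subject is withdrawn and has no other qualifying event, it also loses WOCF.

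**Working it through.** **1. Arm size.** Inputs from Protocol 5.2: 70% versus 30%, two-sided alpha 0.05, 80% power, 20% discontinuation. With pooled variance under the null, n = [1.96·√(2·0.5·0.5) + 0.8416·√(0.21 + 0.21)]² / 0.40² = (1.386 + 0.545)² / 0.16 = 23.3, so 24 per arm. Then 48/0.8 = 60, or 30 per arm. The stated figures reproduce and are not in dispute. One subject is 1/30 = 3.3 points of an arm's response rate.

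**2. Route through the texts for an outpatient withdrawal.**

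| Step | Source | Result |
|---|---|---|
| Worsening unresponsive at 6 weeks, no admission | Protocol 3.3.3 | Withdrawn |
| Is the worsening an adverse event? | Protocol 4.4.7.3 | No |
| Serious MG adverse event present? | SAP 7.3 | Not from this episode |
| Imputation | SAP 7.3, 16.1.2 | LOCF |
| Protocol classification | Protocol 5.1.3.1 | Non-responder |

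The sensitivity analyses in SAP 16.1.4 are a per-protocol repeat and an observed-case analysis. The first keeps the SAP imputation and the second drops subjects with no Week 39 dose. Neither applies the protocol rule.

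**3. Can LOCF give a responder?** Inputs: Table 3-1 (minus 10 mg above 40 mg/day, otherwise minus 5 mg, every three weeks from Week 9) and Table 3-3 (plus 20 mg at 15 mg/day or more, otherwise plus 15 mg). Daily dosing, baselines 15 to 60 mg in 5 mg steps. Worsening is found at a visit from Week 12 to Week 30, and withdrawal follows two visits later, at Week 36 at the latest. That is 10 baselines × 7 visits = 70 paths. The carried value is the increased dose.

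| Baseline | Worsening found | Dose then | Raised to | Reduction |
|---|---|---|---|---|
| 30* | Week 27 | 0 | 15 | 50.0% |
| 30* | Week 30 | 0 | 15 | 50.0% |
| 35* | Week 30 | 0 | 15 | 57.1% |
| 40 | Week 30 | 5 | 20 | 50.0% |
| 45 | Week 30 | 5 | 20 | 55.6% |
| 50 | Week 30 | 10 | 25 | 50.0% |
| 55 | Week 30 | 10 | 25 | 54.5% |

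*Only if the optional step to 0 mg was taken.

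Seven of 70 paths give a responder, four of them without the optional step. Baselines 15, 20, 25 and 60 never do; for 60 at Week 30, 15 + 20 = 35 mg, a 41.7% reduction. Worked case, baseline 40: 35 mg from Week 9, then 5 mg less at each visit, reaching 5 mg at Week 27. Worsening at Week 30 gives 5 + 15 = 20 mg. The subject is unresponsive and withdrawn at Week 36; LOCF carries 20 mg, and (40 − 20)/40 = 50%. WOCF would carry at least 40 mg, a 0% reduction.

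**4. Condition on step 3.** Early-termination averages, and an unscheduled record after the last scheduled visit, are LOCF-eligible (SAP 6.4, 7.3, 16.1.1). A further rise of 5 mg/day in the last such average removes all seven paths: 25/40, 25/45, 30/50, 30/55, 20/30 and 20/35 all exceed one half.

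**5. Second-episode route.** On the same grid 30 of 210 paths give a responder if the carried value is the dose before the second increase. Example: baseline 20, worsening at Week 18 on 5 mg, raised to 20, tapered to 15 (Week 24) and 10 (Week 27), second episode at Week 30; 10 mg is 50%. If a Table 3-3 increase is recorded in full at early termination, none remains.

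**6. Exploratory endpoints.** Assume 1 to 4 MG admissions in an arm of 30 (3.3% to 13.3%). Each unflagged one removes 3.3 points; for example, 4/30 = 13.3% becomes 3/30 = 10.0%.

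**The case against.** - **The SAP's choice was deliberate.** Its modification history records sponsor feedback on WOCF, and Protocol 5.1 leaves data handling to the SAP. That supports the sponsor's right to change the rule. It does not explain why SAP 3.3 omits the change, or why a reason is listed that the next criteria cancel for outpatients.
- **Later dose records would usually correct LOCF.** Withdrawn subjects are asked to attend an Early Discontinuation Visit and two follow-up visits at which the steroid dose is recorded. This stands. The seven paths hold only without a higher later record, and the second-episode paths only if the increase that triggers withdrawal goes unrecorded. A reader might infer from step 5 that the second-episode route is a broad problem; it is not if that increase is captured.
- **An outpatient withdrawal can still qualify for WOCF.** This also stands. SAP 7.3 asks for at least one qualifying MG event, not the one that caused withdrawal. The defect is limited to subjects with no MG admission or MG death during the study.
- **The seriousness conflict may resolve itself.** Protocol 4.4.7.3 is specific to MG and categorical, and 4.4.6 lets either the sponsor or the investigator make an event serious. That is a fair reading, but no text states it, and 4.4.9 defines reportable events by 4.4.6: "Any SAE (see Section 4.4.6) that occurs after". A reader might infer that SAEs will go unreported, or that every exempted admission is a missed crisis. The first follows only if a site applies 4.4.6.1 over 4.4.7.3. The second is not supported: "Myasthenic (or MG) crisis will be defined as an episode of worsening (as defined in Section 3.3.3) which requires hospitalization", so a QMG rise of at least 4 points is also needed.

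**Conclusion.** The primary-endpoint defect holds. The SAP narrows the protocol's non-responder rule, does not declare this, passes it to the secondary percent-reduction endpoint, and plans no analysis under the protocol rule.

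The reach is limited. Most affected subjects are non-responders under either rule. Counts of 7 in 70 and 30 in 210 are counts of protocol-conforming paths, not probabilities, and rest on daily dosing and on no higher dose being captured later. The documents give no number of affected subjects. Each one reclassified moves its own arm by 3.3 points if 30 are analysed. A reader might infer a loss of power or a bias towards one arm. The documents support neither, because the direction depends on which arm the discontinuers come from.

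The seriousness conflict is real but secondary. It bears on two exploratory endpoints whose p-values SAP 16.3.3 describes as informational, and on the primary endpoint only through an admitted subject left unflagged.

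**What to change.** 1. **SAP 7.3 and 16.1.2, before unblinding.** Treat subjects with either of the two MG discontinuation reasons as non-responders (WOCF), with no adverse-event or seriousness condition. Keep the MG adverse-event criteria for the reasons of adverse event and death. SAP 16.2.2.1 then follows.
2. **SAP 3.3 and 16.1.4.** List any remaining departure from Protocol 5.1.3.1 and run the protocol rule as a sensitivity analysis.
3. **Protocol 4.4.6.1 and 4.4.7.3.** Reconcile them so that one rule governs MG admissions, and have 4.4.9 refer to it.
4. **SAP 16.3.1.6 and 16.3.1.7.** In addition to flagged events, count, in the time window of the event, subjects discontinued for MG crisis needing hospitalisation. Also count MG-term adverse events with hospitalisation confirmed at blinded review that meet the worsening definition in Protocol 3.3.3 and 3.3.5. The worsening condition keeps routine admissions out.

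Items 1, 2 and 4 are short SAP edits; items 1 and 4 use discontinuation reasons already recorded. Item 3 is one sentence or a site letter, and possibly a few more SAE reports. SAP 4.1 describes safety review during conduct in the past tense, so item 3 may reach few remaining subjects. The SAP edits do not depend on it.

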4.4.7 Adverse Events of Special Interest

4.4.7.1 Thromboembolic Events

Subjects will be monitored for signs and symptoms of arterial and venous thromboses. In addition, the Grifols Medical Monitor will routinely review reported AEs for possible thromboses. Arterial and venous thromboses will be identified according to definitions in the International Classification of Diseases, Ninth Revision, Clinical Modification (ICD-9-CM). Such thrombotic events include, but are not limited to, DVT, PE, myocardial infarction, cerebrovascular accident, acute coronary syndrome, limb thrombosis, sagittal sinus thrombosis, and portal vein or mesenteric artery thrombosis. All thrombosis will be recorded as AEs, reported accordingly, and if serious, may require early discontinuation from study. See Appendix 7 for details.

4.4.7.2 Hemolysis

Subjects will be monitored for signs and symptoms of hemolysis. In addition, Grifols Medical Monitor will routinely review reported AEs for possible hemolysis. Hemolysis will be recorded as an AE, and reported accordingly, and if resulting in serious hemolytic anemia, may require early discontinuation from study. See Appendix 8 for details.

4.4.7.3 MG Events That Are Not Considered AEs

Given that variations in symptoms are an inherent part of the natural history of MG, all recorded information regarding severity of MG manifestations will be considered efficacy data.

For the purpose of this study, variation in MG symptoms will not be considered an AE unless an exacerbation of MG, or MC requires hospitalization. If a subject is hospitalized for MG, it will be reported as an SAE.

4.4.8 Procedures for Eliciting Reports of and for Recording and Reporting Adverse Events and Suspected Adverse Drug Reactions

The occurrence and follow-up details of all AEs experienced by any of the subjects during the clinical trial, from signature of the *Clinical Trial Written Informed Consent Form* to the last follow-up visit, will be recorded on the AE eCRF entry and in the subject's medical record. If no AE has occurred during the study period, this should also be indicated in the eCRF.

At each visit, AEs will be elicited by asking the individual a non-leading question such as "Do you feel different in any way since the last visit?" Moreover, AEs will also be collected through directly observed events or spontaneously volunteered by the subject. Clearly related signs, symptoms and abnormal diagnostic procedures should preferably be grouped together and recorded as a single diagnosis or syndrome wherever possible. It is responsibility of the investigator to ensure that AEs are appropriately recorded.

The following variables must be recorded on the AE eCRF entry:

- 1. the verbatim term (a diagnosis is preferred)
- 2. date/time of onset
- 3. date/time of resolution
- 4. severity (mild, moderate, severe)
- 5. causality (unrelated, doubtful/unlikely, possible, probable, definite)*
- 6. seriousness (yes, no)
- 7. action taken (with regard to IP)
- 8. other action (to treat the event)
- 9. outcome and sequel (follow-up on AE) *AEs occurring before subject's exposure to IP will be always labeled as "unrelated."

For AEs that occur during infusions, the infusion rate in effect at the time of onset of the AE, the time of onset of the AE and the time of AE change materially in intensity and/or resolves will be captured the eCRF entry.

In addition to the investigator's own description of the AEs, each AE will be encoded by the Sponsor or CRO according to the Medical Dictionary for Regulatory Activities (MedDRA®).

For example, a laboratory test abnormality considered clinically relevant, e.g., causing the subject to withdraw from the study, requiring treatment or causing apparent clinical manifestations, or judged relevant by the investigator, should be reported as an AE. Each event must be described in detail along with start and stop dates, severity, relationship to IP, action taken and outcome. Each event must be adequately supported by documentation as it appears in the subject's medical or case file.

A pregnancy not verified before the Baseline visit but occurring during the course of the study will be not considered an AE, unless a relation to the study drug is suspected. In any case, a *Pregnancy Report Form* must be completed and sent as soon as possible to the Sponsor, and the study treatment must be discontinued. A copy of the form should be filed at the study site for follow-up until the end of the pregnancy.

[figure not shown]

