4.4.1 Adverse Event

An AE is defined as any untoward medical occurrence in a patient or clinical investigation subject administered a medicinal product or study treatment and which does not necessarily

have a causal relationship with this administration. An AE can therefore be any unfavorable and unintended sign (including any abnormal laboratory finding, for example), symptom or disease temporally associated with the use of a medicinal product, whether or not considered related to the medicinal product.

Any AE that occurs at any time between the signature of the ICF and last day of the subject's participation in the clinical trial must be reported and recorded on the AE eCRF entry.

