### 7.3. MISSING DATA

Imputation for missing values will be applied to continuous efficacy endpoints using the LOCF or the WOCF method.

Primary efficacy endpoint of CS dose:

For the primary efficacy endpoint of CS dose, the WOCF method will be applied to subjects who discontinued early from the study with adverse outcomes related to MG, defined as those subjects who met ALL criteria below:

- The primary reason for discontinuation is one of the following: “Adverse Event”, “Death”, “Discontinuation due to MG crisis requiring hospitalization”, or “MG worsening (CS-unresponsive or 2nd episode)”
- The subject had at least one adverse event (AE) with preferred term (PT) of either “Myasthenia gravis crisis” or “Myasthenia gravis”
- The AE is serious, with the reason for seriousness being “Required/Prolonged Hospitalization” or “Resulted in Death”
- The onset date/time of the AE is on or after the start date/time of the first infusion of study medication, i.e., the AE is treatment-emergent

For these subjects, the worst values, i.e., the highest average daily CS dose available among all eligible visits [including the Baseline visit, all post-baseline scheduled visits, and the Early Termination visit(s)], will be carried forward to impute the missing CS dose for all remaining visits.

For subjects who discontinued the study early due to any other reasons, the LOCF method will be used to impute the missing values, i.e., the last non-missing post-baseline CS dose value available among all eligible visits [including all post-baseline scheduled visits and the Early Termination visit(s)] will be carried forward to impute missing values for all remaining visits.

Note for the primary efficacy endpoint of CS dose, the values to be considered as candidates for carrying forward are the derived average daily CS dose at the relevant scheduled visits, incorporating potential changes in the prescribed CS dose within the prior 3 weeks (see section 16.1.1 for derivation details).

Other continuous efficacy variables:

For all other continuous efficacy variables and for all subjects who discontinued the study early, regardless of the reason, the LOCF method will be used to impute the missing values, i.e., the last non-missing post-baseline value (including scheduled, unscheduled, and early termination) will be carried forward to impute missing values for all remaining visits.

All continuous efficacy variables:

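### Protocol 4.4.7.3 gives a serious, non-fatal MG exacerbation without hospital admission no stated route to AE or SAE recording

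*Protocol*

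**What the plan says.** Protocol 4.4.7.3 starts from the natural variability of MG and concludes that "all recorded information regarding severity of MG manifestations will be considered efficacy data". It then sets the condition for AE status: "variation in MG symptoms will not be considered an AE unless an exacerbation of MG, or MC requires hospitalization". On seriousness it adds: "If a subject is hospitalized for MG, it will be reported as an SAE".

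The general rules are wider. Section 4.4.1 reads "An AE is defined as any untoward medical occurrence in a patient or clinical investigation subject administered a medicinal product or study treatment" and contains no exception for the disease under study. Under section 4.4.6 an AE or suspected ADR is serious if, "in the view of either the investigator or Sponsor, it results in any of the following outcomes", and six alternatives follow. One is a life-threatening event, which "refers to an event in which the subject was at risk of death at the time of the event". Another is the important medical event, worded to take in events that need not lead to hospitalization. Section 4.4.9 requires SAEs as defined in 4.4.6 to reach the sponsor within 24 hours.

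Two further passages bear on the one open route. Section 3.3.5 defines myasthenic crisis as worsening that needs hospitalization. Section 4.4.6.1 says a hospitalization is not serious when the investigator regards it as part of clinical practice for treating MG.

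In SAP 7.3, one condition for carrying the worst dose forward is "The AE is serious, with the reason for seriousness being" either hospitalization or death. SAP 4.1 limits the safety committee's review to listings of AEs, SAEs, discontinuations due to AEs and laboratory data, without efficacy data.

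**The concern.** Worsening MG is the foreseeable harm of the steroid taper. Section 3.3.3 itself warns that in subjects tapered to 0 mg "deterioration can be of greater severity and speed than expected and may be difficult to reverse". A rule that admits such an event to the safety record through one seriousness outcome only leaves a gap where harm is most expected.

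At stake are the 24-hour report, the serious-TEAE table, the AE-based discontinuation listing and what the safety committee sees. If worsening is more frequent in one arm, under-recording is probably more frequent there too, and the safety contrast between arms would be blunted. That direction is a reasoned expectation; the documents give no data on it.

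**Working it through.** No figure in the plan can be reproduced here, so the check is a comparison of the texts, case by case.

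| MG event | Section 4.4.7.3 | Sections 4.4.1 and 4.4.6 | Result |
|---|---|---|---|
| Hospitalized | AE and SAE | AE; serious, unless 4.4.6.1 exempts the admission | 4.4.6.1 and 4.4.7.3 contradict each other |
| Life-threatening, not admitted | No exception named | AE; serious | Gap |
| Persistent incapacity, not admitted | No exception named | AE; serious | Gap |
| Medically important, not admitted | No exception named | AE; serious | Gap |
| Fatal, not admitted | No exception named | AE; serious | Unclear |

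Four points settle the reading.

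1. **Scope of the exclusion.** The sentence in 4.4.7.3 makes exacerbations requiring hospitalization an exception to symptom variation. Other exacerbations therefore stay inside the exclusion, and it cannot be confined to day-to-day fluctuation.
2. **Where the conflict lies.** Section 4.4.6 classifies something that is already an AE or suspected ADR. Section 4.4.7.3 acts one step earlier, on whether the event is an AE at all. The direct conflict is therefore with 4.4.1; the seriousness criteria and the duty in 4.4.9 are bypassed as a consequence. No passage says that 4.4.6 overrides 4.4.7.3.
3. **Deaths.** Section 4.4.7.3 does not mention death. Protocol 5.1.4 lists and narrates subjects with deaths without an MG exception, and SAP 7.3 has death both as a discontinuation reason and as a seriousness reason for MG-coded AEs. The documents thus expect deaths to be captured, without saying how an MG death outside hospital becomes an AE.
4. **What is captured elsewhere.** A QMG rise of at least 4 points counts towards time to worsening (SAP 16.2.1.2) and the number of episodes (SAP 16.3.1.8), with unscheduled assessments included. Withdrawal reasons are recorded (Protocol 3.10), and MG worsening is a category of its own in SAP 7.3. These records carry no seriousness, causality or outcome as an AE entry does. At 0 mg, section 3.3.3 also allows steroids to be restarted without a 4-point rise, so such an event could miss the worsening endpoint as well as the AE record.

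For scale only: about 60 subjects randomized 1:1 gives 60/2 = 30 per arm, so one affected subject is 1/30 = 3.3 percentage points of an arm's serious-event incidence.

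**The case against.** The strongest defence is that treating fluctuation of the studied disease as efficacy data is a stated and reasoned choice that keeps AE tables from filling with the outcome itself. Worsening without admission is compared between arms as a secondary endpoint, withdrawals appear in disposition, section 3.3.3 requires prompt clinic evaluation at 0 mg, and the Medical Monitor reviews eCRFs and concomitant medication as well as AEs. All of this stands: information is not simply lost. It does not supply expedited reporting, AE and SAE tabulation or safety committee review.

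A second defence is that the AE condition in 4.4.7.3 speaks of needing hospitalization, and a life-threatening exacerbation would ordinarily need it. That narrows the life-threatening case in practice. It does less for incapacity and for important medical events, which 4.4.6 treats as serious on other grounds.

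Two stronger readings are tempting. A reader might infer that fatal MG events are never recorded; Protocol 5.1.4 and SAP 7.3 do not support that. A reader might also infer that SAP 7.3 contradicts 4.4.7.3 by expecting MG AEs that are serious because of death. The two are compatible for a subject who is admitted and then dies, and SAP 7.3 does not say that the death occurs without admission.

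**Conclusion.** The gap is real but narrow. It concerns non-fatal MG exacerbations without admission that are life-threatening, incapacitating or medically important. For MG deaths without admission the documents are unclear, and no more than that can be claimed. Separately, 4.4.6.1 and 4.4.7.3 contradict each other on whether a hospitalization for MG is serious, so even the open route needs repair.

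The documents give no rate for such events, and the judgement that they are few is an assumption. Supposing a range such as 0 to 3 events in one arm, or up to 3/30 = 10 percentage points, would be a guess without a source in the documents and is no evidence of importance. The 3.3 points per subject rests on about 30 treated subjects per arm. This is a cheap improvement to safety reporting; it does not call the efficacy analyses into question.

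**What to change.** In Protocol 4.4.7.3, keep the sentence under which a subject hospitalized for MG is reported as an SAE. Add that an MG event meeting any other seriousness criterion in 4.4.6 (death, life-threatening, incapacity or important medical event) is also recorded as an AE and reported as an SAE with that reason.

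The new text must be added, not substituted. Replacing the existing sentence with a general reference to 4.4.6 would bring in the exemption in 4.4.6.1 and could drop MG admissions that are captured now. In the same edit, reconcile 4.4.6.1 with 4.4.7.3 so that both say the same about hospitalization for MG.

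The cost is this short edit, a line in site training and a few more SAE forms. No treatment, visit or assessment changes.
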